**Table 1 Schedule of Assessments**

Schedule of Assessments	Screening Period			Randomization	Treatment Period			Follow-Up Period a	
	Screening	Wash-out	Baseline Diary Run-In dd		Treatment			Follow-up Visit	End of Study (EOS) Phone Call
Visit	1	NA	2	3	4	5	6	7	N/A
Week		-6 through -1			2	4	8/EOT	10	12
Day (and Window)		-42 to -8		1	15 ± 2	29 ± 2	57 ± 2	71 ± 2	85 ± 2
ASSESSMENTS									
Informed Consent	X								
Demographics	X								
Height and Weight b	X			X		X	X		
Medical/Surgical History	X		X c						
Medication History and Concomitant Medication	X								
FM Diagnosis (ACR 1990 & 2010)	X								
Verify Eligibility Criteria (and duplicate subject database check)	X	X d	X d	X					
Phone Call to Subject e		X							X
e-diary Distribution/Return			X					X	
Physical Examination (including tender point exam at screening)	X			X			X	X	
Drug and Alcohol Screen f	X		X	X					
Randomization g				X					
Vital Signs h	X			X	X	X	X	X	
Laboratory Tests (Hematology, Biochemistry, Urinalysis) i	X			X	X	X	X	X	
Electrocardiogram j	X			X			X	X	
Pregnancy Test	X k			X l			X l	X l	
Blood Sample for Pharmacogenomics m				X					
Blood sampling for Pharmacokinetics n				X	X	X	X		

Table continued on next page

Schedule of Assessments	Screening Period			Randomization	Treatment Period			Follow-Up Period a	
	Screening	Wash-out	Baseline Diary Run-In dd		Treatment			Follow-up Visit	End of Study (EOS) Phone Call
	Visit	1	NA	2	4	5	6		
Week	-6 through -1				2	4	8/EOT	10	12
Day (and Window)	-42 to -8		-7 to -1	1	$15 \pm 2$	$29 \pm 2$	$57 \pm 2$	$71 \pm 2$	$85 \pm 2$
ASSESSMENTS									
CMSI			X						
MINI o	X								
HADS p	X			X			X		
NRS e-diary Collection q				←	█	█	█	→	
PGIC s					█	X	X	X	X
PGIS t				X	█	█	█	█	X
FIOR x	X			←	█	X	X	X	X
C-SSRS	X				█			█	
Subject Training Materials aa	X		X		X	X	X	X	X
Study Drug Dispensed					X	X	X		
Study Drug Dosing bb					X	X	X	X	
Study Drug Returned						X	X	X	
Adverse Events cc	←								→
Rescue Medication (if applicable)			←						→

- a) Follow-up visit and phone call will be planned relative to date of last dose (14 and 28 days post last dose).

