- z) Columbia Suicide Severity Rating Scale (C-SSRS). Questionnaire will be facilitated by the Principal Investigator/Site staff, as appropriately trained, at screening, randomization, weeks 2, 4, 8/EOT, and week 10/follow up visits.
- aa) Subject Training Materials are to be distributed and reviewed during the screening period.
- bb) Subjects will begin study drug dosing on day 1 of the randomization visit.
- cc) (Serious) Adverse Events will be collected from the time of signing the informed consent through 4 weeks post-last dose.
- dd) The baseline diary run-in may be extended up to 2 days if necessary in the Investigator's opinion. In general, the Screening period should not exceed 42 days.

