### **5.5    Adverse Events and Other Safety Aspects**

#### **5.5.1    Definition of Adverse Events**

An AE is any untoward medical occurrence in a subject, temporally associated with the use of a medicinal product, whether or not considered related to the medicinal product. An AE can therefore be any unfavorable and unintended sign (including an abnormal laboratory finding), symptom, or disease (new or exacerbated) temporally associated with the use of a medicinal product.

In order to identify any events that may be associated with study procedures and could lead to a change in the conduct of the study, Astellas collects AEs even if the subject has not received treatment. AE collection begins after the signing of the informed consent and will be collected until 30 days after the last dose of study drug.

An abnormality identified during a medical test (e.g., laboratory parameter, vital sign, ECG data, physical examination) should be defined as an AE only if the abnormality meets 1 of the following criteria:

- Induces clinical signs or symptoms
- Requires active intervention
- Requires interruption or discontinuation of study drug
- The abnormality or test value is clinically significant in the opinion of the investigator.

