#### **5.5.6 Reporting of Serious Adverse Events**

The collection of AEs and the expedited reporting of SAEs will start following receipt of the informed consent and will continue to 30 days after the last dose of study drug.

In the case of a SAE, the investigator must contact the Sponsor by fax or email immediately (within 24 hours of awareness) and the study team (CRA and Medical Monitor) should be notified as well within 24 hours of awareness.

The investigator should complete and submit an SAE/Special Situation Worksheet containing all information that is required by local and/or regional regulations to the Sponsor by email or fax immediately (within 24 hours of awareness).

For contact details, see [Section II Contact Details of Key Sponsor's Personnel]. Fax or email the SAE/Special Situations Worksheet to:

If there are any questions, or if clarification is needed regarding the SAE, please contact the Sponsor's Medical Monitor/Study Physician or his/her designee [Section II Contact Details of Key Sponsor's Personnel].

Follow-up information for the event should be sent promptly (within 7 days of the initial notification).

Full details of the SAE should be recorded on the medical records, SAE/Special Situation Worksheet and on the (e)CRF.

The following minimum information is required:

- International Study Number (ISN)/Study number,
- Subject number, sex and age,
- The date of report,
- A description of the SAE (event, seriousness criteria),
- Causal relationship to the study drug, and

The Sponsor or Sponsor's designee will submit expedited safety reports (e.g., IND Safety Reports, Council for International Organizations of Medical Sciences-I) to the regulatory agencies (e.g., FDA, EMA) per current local regulations, and will inform the investigators of such regulatory reports as required. Investigators must submit safety reports as required by their Institutional Review Board (IRB) within timelines set by regional regulations (e.g., EU, (e)CTD, FDA) where required. Documentation of the submission to and receipt by the IRB of expedited safety reports should be retained by the site.

The Sponsor will notify all investigators responsible for ongoing clinical studies with the study drug of all SUSARs which require submission per local IRB requirements.

The investigators should provide written documentation of IRB notification for each report to the Sponsor.

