### 7.5.1 Adverse Events

AEs will be coded using the MedDRA. Treatment Emergent Adverse Event (TEAE) is defined as any AE which starts, or worsens, after the first dose of study drug through 30 days after the last dose of study drug.

The number and percentage of subjects with TEAEs, TEAEs leading to discontinuation, serious TEAEs and TEAEs related to study drug as assessed by the investigator will be summarized by system organ class, preferred term and treatment group. In addition, TEAEs will be summarized by relationship to study drug as determined by the investigator and by severity for each treatment group.

All TEAEs will also be listed.

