- z) Columbia Suicide Severity Rating Scale (C-SSRS). Questionnaire will be facilitated by the Principal Investigator/Site staff, as appropriately trained, at screening, randomization, weeks 2, 4, 8/EOT, and week 10/follow up visits.
- aa) Subject Training Materials are to be distributed and reviewed during the screening period.
- bb) Subjects will begin study drug dosing on day 1 of the randomization visit.
- cc) (Serious) Adverse Events will be collected from the time of signing the informed consent through 4 weeks post-last dose.

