## 6.2.1 Adverse Events

Adverse events will be categorized as those which occur prior to first dose or treatment-emergent as follows:

- Adverse events prior to first dose  
Adverse events prior to first dose is an adverse event which starts prior to the first dose of study drug. If the adverse event occurs on Day 1 and the onset check box is marked “Onset before first dose of study drug”, then the adverse event will be considered as an AE prior to first dose. If the adverse event occurs on Day 1 and the onset check box is marked “Onset after first dose of study drug” or the onset check box is left blank, then the adverse event will not be considered as an AE prior to first dose.
- Treatment-emergent adverse events (TEAEs; frequency, severity, seriousness, and relationship to study drug).

TEAE is defined as an adverse event which starts, or worsens, after the first dose of study drug through 30 days after the last dose of study drug. If the adverse event occurs on Day 1 and the onset check box is marked “Onset after first dose of study drug” or the onset check box is left blank, then the adverse event will be considered treatment emergent. If the adverse event occurs on Day 1 and the onset check box is marked “Onset before first dose of study drug”, then the adverse event will not be considered treatment emergent, unless it worsens in severity after Day 1 (up to day 30 after last dose).

TEAE (Treatment period) is an adverse event which starts, or worsens, after the first dose of study drug through to 4 days after the last dose of study drug. If the adverse event occurs on Day 1 and the onset check box is marked “Onset after first dose of study drug” or the onset check box is left blank, then the adverse event will be considered treatment emergent. If the adverse event occurs on Day 1 and the onset check box is marked “Onset before first dose of study drug”, then the adverse event will not be considered treatment emergent, unless it worsens in severity after Day 1 (up to day 4 after last dose).

TEAE (Follow-up period) is an adverse event which starts, or worsens, 5 days after the last dose of study drug through 30 days after the last dose of study drug.

A drug-related TEAE is defined as any TEAE with a possible or probable relationship to study treatment as assessed by the investigator or with missing assessment of the causal relationship.

For each AE, duration will be calculated in days, using the following formula:

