**Definition of Safety Follow-up Period:**

Time from Follow-up Day 5 through to Follow-up Day 30.

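### Table 1 ends AE/SAE collection at 4 weeks after the last dose while the protocol text and SAP run to 30 days, and the last scheduled contact leaves 0 to 4 days of the TEAE window uncovered

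*Protocol*

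**What the plan says.** Two end dates stand in the current text.

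**Four weeks (28 days)**
- Protocol Table 1, footnote cc: "Serious) Adverse Events will be collected from the time of signing the informed consent through 4 weeks post-last dose". SAP Table 1, footnote cc, repeats it: "from the time of signing the informed consent through 4 weeks post-last dose".
- The safety endpoint (Protocol Synopsis and 2.3.1) runs from Screening to EOS. The key-term definitions in both documents put the last protocol-defined assessment at about 4 weeks after the last dose.

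**Thirty days**
- Protocol 5.5.1: "AE collection begins after the signing of the informed consent and will be collected until 30 days after the last dose of study drug".
- Protocol 5.5.6, on AE collection and expedited SAE reporting: "will continue to 30 days after the last dose of study drug".
- Protocol 7.5.1 counts as treatment-emergent any event that starts or worsens "after the first dose of study drug through 30 days after the last dose of study drug". The SAP key terms and SAP 6.2.1 give the same limit.
- SAP 6.2.1, follow-up TEAEs: "5 days after the last dose of study drug through 30 days after the last dose of study drug".
- SAP 7.1, safety follow-up period: "Time from Follow-up Day 5 through to Follow-up Day 30".

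**Last contact**
- Protocol Table 1, footnote a: "Follow-up visit and phone call will be planned relative to date of last dose (14 and 28 days post last dose". The EOS column allows Day 85 ± 2. No later contact is scheduled.

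**The concern.** A site working from Table 1 has a collection period that ends two days before the one in 5.5.1 and 5.5.6. Whether an event with onset on Day 29 or 30 is recorded can depend on which section the site follows. The same ambiguity applies to expedited SAE reporting, at up to about 35 sites.

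Separately, the analysis counts events to Day 30, while the last planned question to the subject is normally asked on Day 28 and may be asked on Day 26. Events after the call can enter the tables only if the subject volunteers them or the site learns of them in some other way.

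Safety and tolerability is a primary objective. The SAP also tabulates follow-up TEAEs separately and summarizes withdrawal-related events in the follow-up period, so the end of this window is used in planned output.

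**Working it through.** **Inputs**
- End of treatment: Day 57 (Protocol Synopsis and 2.2.1), taken as the day of the last dose.
- EOS call: 28 days after the last dose, Day 85 ± 2 (Table 1 and footnote a).
- End of TEAE window: 30 days after the last dose (Protocol 7.5.1, SAP 6.2.1).
- Follow-up TEAE window: Follow-up Days 5 to 30 (SAP 6.2.1 and 7.1).

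**Step 1. Reproduce the plan's call day.** 57 + 28 = 85, as stated.

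**Step 2. Range of the call.** 28 ± 2 gives Follow-up Day 26 to 30 (Study Day 83 to 87).

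**Step 3. Window lengths.** Follow-up TEAE window: 30 − 5 + 1 = 26 days. Whole TEAE window for a completer: Day 1 to Day 57 + 30 = 87, which is 87 days.

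**Step 4. Days after the last contact.** Uncovered days = 30 − (follow-up day of the call), counting the call day as covered.

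| Call on follow-up day | Uncovered days | Share of 26 days | Share of 87 days |
|---|---|---|---|
| 26 | 4 | 15.4% | 4.6% |
| 27 | 3 | 11.5% | 3.4% |
| 28 (target) | 2 | 7.7% | 2.3% |
| 29 | 1 | 3.8% | 1.1% |
| 30 | 0 | 0% | 0% |

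**Step 5. Sensitivity to the last-dose day.** If the last dose fell on Day 56 and the call were held to Day 85 ± 2, the call would be on Follow-up Day 27 to 31 and the gap 0 to 3 days. Footnote a ties the call to the date of last dose, so 26 to 30 is the better reading.

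**Step 6. Does call timing cure the conflict?** No. Footnote cc stops at Day 28 and 5.5.1 and 5.5.6 stop at Day 30, so for 30 − 28 = 2 days the instructions differ whenever the call is made. A site that calls on Day 30 but follows footnote cc has no instruction there to record an event from Day 29.

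**Step 7. Could 30 days be loose wording for 4 weeks?** The SAP suggests not. Section 7.1 ends efficacy follow-up at Follow-up Day 28 and safety follow-up at Follow-up Day 30, so it treats them as different limits.

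**The case against.** The case against giving this much weight is substantial, and most of it stands.

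- **SAE reporting.** A reader might infer that an SAE on Day 29 or 30 would breach the 24-hour rule. It would not: the clock in 5.5.6 runs from awareness. Protocol 5.5.7 also provides for AEs that occur after a subject has discontinued the study, and requires immediate reporting of a new SAE that arises during AE follow-up. The gap is in planned questioning.
- **Size.** Quoting only the 26-day denominator flatters the finding. Against the whole TEAE window, the target-day gap is 2.3%.
- **Consequence.** The call schedule is the same in both arms, and safety is descriptive with no hypothesis tests (Protocol 7.5, SAP 7.5). With a mean half-life of about 65 hours (Protocol 1.2), Day 28 is 28 × 24 / 65 ≈ 10 half-lives after the last dose.
- **A 30-day counting limit is not wrong in itself.** The latest permitted call is on Day 30, so this limit admits every event reported at any in-window call.

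Three stronger readings are tempting but unsupported. One is that most subjects would lack 30-day follow-up; the documents give no distribution of call days, and a Day 30 call leaves no gap. Another is that table titles would overstate follow-up; no table shells are shown. The third is that sites stop collecting at the call; footnote cc says through 4 weeks, so a site calling on Day 26 still collects to Day 28.

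None of this removes the conflict between footnote cc and 5.5.1/5.5.6, or gives the end of the window a contact when the call is on target or early.

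**Conclusion.** The inconsistency is real, and the SAP also contradicts itself (its footnote cc against its 6.2.1 and 7.1). Between 0 and 4 days of the TEAE window follow the last scheduled contact, 2 on target: 8% of the follow-up TEAE window and 2.3% of the whole window, at worst 15% and 4.6%. These figures assume a last dose on Day 57 and a call inside its stated window.

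The likely effect on TEAE counts is small and not differential by design, and the efficacy analysis is untouched. It should still be corrected, because sites should not hold two end dates for AE collection and expedited SAE reporting in a trial with safety as a primary objective, and the correction is cheap.

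**What to change.** Use the 30-day period, which 5.5.1, 5.5.6, 7.5.1 and the SAP already state.

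1. Change footnote cc to 30 days in Table 1 of both documents.
2. Schedule the EOS call no earlier than 30 days after the last dose, for example Day 87 with a window of 0 to a few days later.
3. Make the matching edits: Table 1 footnotes a and e, the Table 1 EOS column and the flow chart in both documents; the EOS definition in the protocol and SAP key terms; and the Day 85 text in the Synopsis and Protocol 2.2.1. The safety endpoint and the recording of concomitant medication are tied to EOS and would follow without rewording.

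Cutting everything to 28 days would also remove the contradiction, but it shortens the stated AE and SAE collection. With the present ± 2 window, a call 1 or 2 days early would still leave 1 or 2 days uncovered.

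**Cost.** The same phone call a few days later, no new visit, and a protocol amendment with matching SAP text. The amendment should not be assumed to be administrative: Protocol 8.3.3 requires IRB approval before a change that affects the evaluation of safety. Other requirements that run to EOS, such as the prohibited-therapy period, would lengthen by the same few days unless the sponsor words them separately.

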## 1 INTRODUCTION

Protocol 8062-CL-0101 is a proof-of-concept study to examine the effects of ASP8062 for the treatment of pain in subjects with fibromyalgia.

### 1.1 Background

#### Background on Target Indication

Fibromyalgia is a complex syndrome characterized by chronic widespread musculoskeletal pain often occurring with symptoms of depression, fatigue, sleep disturbances and/or cognitive complaints. Fibromyalgia pain typically includes deep musculoskeletal pain with tender points in the shoulder, girdle, torso, hips and extremities. Fibromyalgia may include various somatic symptoms, such as headache and irritable bowel syndrome. The core diagnostic criteria for fibromyalgia are defined by the 1990 American College of Rheumatology (ACR) [Wolfe et al, 1990]. While the ACR has published new, as well as subsequent amended criteria [Wolfe et al, 2011; Wolfe et al, 2010], the 1990 version is still commonly utilized in clinical trials. The overall prevalence of fibromyalgia in the general population was estimated to be 2.2% in the United States (3.4% and 0.5% in females and males, respectively) [Queiroz, 2013].

Drugs used to treat fibromyalgia (e.g., pregabalin, duloxetine) provide, at best, only modest relief of symptoms and are accompanied by various side effects including sedation, dizziness, cognitive complaints, weight gain, edema and headaches. The approved medications for the treatment of fibromyalgia (US: pregabalin, duloxetine, milnacipran; Japan: pregabalin) result in only an incremental increase in the percent of subjects (~8% to 13%) with a 30% pain reduction compared to 28% to 34% of subjects with a similar level of improvement on placebo in randomized clinical trials [Häuser et al, 2014]. Despite the available approved medications, novel medications to treat pain, fatigue, sleep disturbances and impaired cognition without intolerable AEs are required to address an unmet medical need for subjects with fibromyalgia.

A pathophysiological mechanism for fibromyalgia has not yet been established. The concept of altered central processing of nociceptive information has dominated the fibromyalgia literature [Woolf, 2011; Staud, 2011]. However, clinical studies support the hypothesis that increased glutamate or decreased GABA within the posterior insula may be related to apparent central sensitization in FM pathophysiology [Foerster et al., 2012; Harris et al., 2009; Harris et al., 2008].

#### Background on Pharmacological Concept

$\gamma$ -aminobutyric acid (GABA), the most abundant inhibitory neurotransmitter, activates 2 types of receptors: ionotropic GABA type A (GABAA) receptors [Olsen & Sieghart, 2008] and metabotropic GABAB receptors [Bowery et al, 2002]. Based on evidence from GABAB receptor agonists (baclofen and sodium oxybate [SXB]), stimulation of GABAB receptors may constitute a putative new target in treating disorders such as fibromyalgia [Russell et al, 2011]. A double-blind, placebo-controlled randomized fibromyalgia clinical trial with the

GABAB receptor agonist SXB provides promise that optimal activation of GABAB receptors might result in clinically significant improvements in efficacy for patients with fibromyalgia compared to currently available treatments [Spaeth et al, 2012; Russell et al, 2011; Russell et al, 2009]. However, the muscle relaxant, bradycardia-inducing and sedative properties of baclofen and SXB limit their potential widespread therapeutic utility [Dario & Tomei, 2004; Chin et al, 1998]. One possible alternative approach is the use of positive allosteric modulator (PAM) [Ong & Kerr, 2005]. They positively modulate the effect of the agonist by binding to an allosteric site without directly stimulating the receptor and are, therefore, expected to exert agonist-like activity with lower incidence of undesirable side effects [May et al, 2004].

Animal studies have established the antinociceptive action of GABAB receptor agonists, probably by effects on both spinal cord and brain [Bowery et al, 2002]. Altered spinal GABA levels may contribute to the induction phase of chronic pain [Eaton et al, 1999]; and lowering GABA levels within the insula is reported to enhance pain in an animal model [Jasmin et al, 2003].

In a clinical study, patients with fibromyalgia had significantly decreased GABA levels in the right anterior insula versus the levels seen in healthy volunteers [Foerster et al, 2012]. Diminished inhibitory neurotransmission resulting from lower concentrations of GABA within the brain may play a role in the pathophysiology of fibromyalgia, suggesting the activation of GABA transmission can be a possible therapeutic approach against fibromyalgia. These concepts are supported by clinical efficacy of SXB on pain, fatigue, sleep disturbance and functionality in fibromyalgia patients [Russell et al, 2011].

#### Rationale for Clinical Trial with ASP8062

ASP8062 is an orally available small-molecule with GABAB receptor-PAM activity discovered by Astellas Pharma Inc. In the reserpine-induced myalgia model, a rat model of fibromyalgia [Nagakura et al, 2009], ASP8062 significantly recovered the decrease in muscle pressure threshold via the potentiation of GABAB receptor function. Based on nonclinical studies, ASP8062 may effectively ameliorate fibromyalgia while minimizing side effects seen with GABAB agonists. Double-blind, placebo-controlled randomized fibromyalgia clinical trials with the GABAB receptor agonist SXB provides promise that optimal activation of GABAB receptors might result in clinically significant improvements in efficacy for patients with fibromyalgia compared to currently available treatments [Spaeth et al, 2012; Russell et al, 2011; Russell et al, 2009].

